6.2. Secondary Objective

The secondary objective is:

- To determine the effect of QD TVB-2640 for 12 weeks versus placebo in subjects with NASH on:
 - Lipid and lipoprotein parameters, including low-density lipoprotein cholesterol (LDL-C), non-LDL-C, high-density lipoprotein cholesterol (HDL-C), non-HDL-C, total cholesterol, TG, apolipoprotein B (ApoB), and lipoprotein(a) (Lp[a]) particles.
 - NASH and fibrosis biomarkers including cytokeratin-18 (CK-18), fibrosis-4 (FIB-4), and enhanced liver function (ELF) or FIBROSpect 2 or ProC3 test.
 - Eicosanoid panel.

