6.4. Endpoints

6.4.1. Efficacy Endpoints

The primary efficacy endpoint is:

- Percent change from baseline in liver fat at Week 12, as determined by MRI-PDFF.

The key secondary efficacy endpoint is:

- The percentage of subjects with at least a 30% reduction in liver fat at Week 12, as determined by MRI-PDFF.

Additional efficacy endpoints are:

- Percent change from baseline in liver fat at Week 16, as determined by MRI-PDFF.
- Percentage of subjects with at least a 30% reduction in liver fat at Week 16, as determined by MRI-PDFF.
- Change from baseline over the 12-week treatment period in:
 - Liver aminotransferases.
 - Lipid and lipoprotein parameters.
 - NASH and fibrosis markers.
 - Eicosanoids.

Exploratory efficacy endpoints are:

- Change from baseline over the 12-week treatment period in:
 - Liver fibrosis, as determined by VCTE.
 - Metabolic parameters.
 - Anthropometric parameters.
 - Lipidomic analyses for DNL.
- Proportion of subjects with <5% liver fat (normalized) at Week 12.

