The primary and key secondary efficacy analyses will be conducted using a fixed-sequence strategy to maintain the overall Type I error rate at 0.05. The primary efficacy analyses will compare the primary efficacy endpoint between each randomized TVB-2640 dose group with the pooled placebo group, each using a 2-sided test at the 0.05 level of statistical significance with the goal of identifying the minimum effective dose. The primary efficacy analyses start with the highest dose-group comparison and if statistically significant, testing will proceed to the low dose group comparison. If both comparisons of the primary efficacy endpoint are significant, then testing will proceed to the key secondary efficacy analyses. The key secondary efficacy analyses will similarly compare the key secondary efficacy endpoint between each randomized TVB-2640 dose group with pooled placebo group, each using a 2-sided test at the 0.05 level of statistical significance. The key secondary efficacy analyses start with the highest dose-group comparison and if statistically significant, testing will proceed to the low dose group comparison.

In the primary and key secondary analyses, missing Week 12 values for MRI-PDFF will be imputed with the last post-baseline observation on or after Week 8 in the mITT. Secondary and sensitivity analyses using other methods for missing data methods and in different analysis populations will be described in the SAP.

For other continuous secondary efficacy endpoints measured at multiple post-baseline visits, the changes at 12 weeks will be summarized for each treatment group and compared between each randomized TVB-2640 dose group and pooled placebo using a linear mixed-effects model for repeated measures in the ITT. The model will include the stratification factor (diabetes

presence/absence), treatment group, visit, and treatment-by-visit interaction as the fixed effects, and baseline value as a covariate using an unstructured variance-covariance matrix. The point estimates for the least-squares mean of the pairwise difference for each randomized TVB-2640 dose group and pooled placebo comparison at each visit and the corresponding 95% confidence interval and two-sided p-value will be summarized. Other variance-covariance structures may be substituted if convergence problems arise.

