Similarly, a generalized linear mixed-effects model for repeated measures based on a logit link function will be used for comparing other categorical efficacy endpoints at Week 12 between each randomized TVB-2640 dose group and pooled placebo in the ITT. The model will include the stratification factor (diabetes presence/absence), treatment group, visit, treatment-by-visit interaction as fixed effects and, depending on the nature of the data, the baseline result as fixed effect or covariate with an unstructured variance-covariance matrix. The point estimates for the least-squares mean of the pairwise difference for each randomized TVB-2640 dose group and pooled placebo comparison at each visit and the corresponding 95% confidence interval and two-sided p-value will be summarized. Other variance-covariance structure may be substituted if convergence problems arise.

Subset analyses will be performed on all efficacy endpoints for subjects enrolled in China to evaluate the consistency of results between subjects enrolled in each country.

Efficacy data will be summarized descriptively for Cohort 3.

Details for handling of data from the US and Chinese subjects will be described in the SAP. Additional details of analysis of other secondary efficacy endpoints and the analysis of exploratory and safety endpoints and pharmacokinetics will be described in the SAP.

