4. STUDY ENDPOINTS

4.1. Efficacy

The primary efficacy endpoint is:

- Percent change from baseline in liver fat at Week 12, as determined by MRI-PDFF.

The key secondary efficacy endpoint is:

- The percentage of subjects with at least a 30% reduction in liver fat at Week 12, as determined by MRI-PDFF.

Additional secondary efficacy endpoints are:

- Percent change from baseline in liver fat at End of Treatment and End of Study, as determined by MRI-PDFF.

Sponsor: Sagimet Biosciences

Protocol Number: 3V2640-CLIN-005

Version and Date: Final Version 1, 02June2020

- Percentage of subjects with at least a 30% reduction in liver fat at End of Treatment and End of Study, as determined by MRI-PDFF.
- Change from baseline over the treatment period in:
 - Liver aminotransferases.
 - Lipid and lipoprotein parameters.
 - NASH and fibrosis markers.
 - Eicosanoids.

Exploratory efficacy endpoints are:

- Change from baseline over the treatment period in:
 - Liver fibrosis, as determined by VCTE.
 - Metabolic parameters.
 - Anthropometric parameters.
 - Lipidomic analyses for DNL.
- Proportion of subjects with <5% liver fat (normalized) at Week 12.

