treatment group, visit, and treatment-by-visit interaction as the fixed effects, and baseline value as a covariate, and the model will use an unstructured variance-covariance matrix. The point estimates for the least-squares mean of the pairwise difference for each TVB-2640 dose group and pooled placebo comparison at each visit and the corresponding 95% confidence interval and two-sided p-value will be summarized. If convergence problems arise when fitting the model, a spatial power covariance structure will be used as a first step. If the model still has convergence issues, compound symmetry covariance structure will be employed.

For the end of study final analysis, if a country-by-treatment interaction is found in the primary efficacy endpoint, the subjects from the US and China in the 50 mg cohort will be analyzed separately. However, if no country-by-treatment interaction is found in the primary efficacy endpoint, the interaction may be explored within the secondary endpoints in a similar manner in order to determine if there is a significant interaction for any of the other endpoints (e.g., ALT or AST).

The model produces asymptotically consistent estimates when data are missing at random. No imputation of missing data will be required for these analyses. By definition, subjects without a baseline and at least 1 post-baseline value will be excluded from the MMRM analyses. Model assumptions (normality of residuals and parallel slopes) may be assessed. If assumptions are not met, then transformations will be done analogous to the primary efficacy analyses described above.

Similar analyses will be performed for:

- Lipid and lipoprotein parameters including low-density lipoprotein cholesterol (LDL-C), non-LDL-C, high-density lipoprotein cholesterol (HDL-C), non-HDL-C, total cholesterol, TG, apolipoprotein B (ApoB), and lipoprotein(a) (Lp[a]) particles, total Cholesterol:HDL ratio, LDL:HDL ratio (Note that the cholesterol and LDL to HDL ratios will be derived and do not come directly from the laboratory)
- NASH and fibrosis biomarkers including cytokeratin-18 (CK-18), fibrosis-4 (FIB-4), and enhanced liver function (ELF) or FIBROspect 2 or ProC3 test.
- Eicosanoids including 5-LOX-derived leukotriene B4 (LTB4), COX-derived prostaglandin E2 (PGE2), and 15-LOX-derived 15-hydroxyeicosatetraenoic acid (15-HETE) and lipoxin A4 (LXA4). For eicosanoids, descriptive statistics will be presented without any statistical testing.

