Analyses and data presentations described in the protocol have been expanded upon, but no other changes were made to analyses specified in the protocol. Any additional changes to the planned analyses as detailed in this SAP will be described in the CSR.

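### SAP 8.3.2 limits eicosanoids to descriptive statistics, although the protocol's rule for such secondary endpoints is an MMRM comparison with pooled placebo, and SAP Section 9 does not list the change.

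*SAP*

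**What the plan says.** **Objective.** Protocol 6.2 states the secondary objective as: "To determine the effect of QD TVB-2640 for 12 weeks versus placebo in subjects with NASH on" three groups of measures, the last being "Eicosanoid panel". SAP 2.2 repeats this.

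**Endpoint tier.** Protocol 6.4.1 puts eicosanoids under "Additional efficacy endpoints are", apart from the exploratory endpoints. SAP 4.1 puts them under "Additional secondary efficacy endpoints are".

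**Protocol analysis.** Protocol 13.2.2 sets a rule by class: "For other continuous secondary efficacy endpoints measured at multiple post-baseline visits, the changes at 12 weeks will be summarized for each treatment group". The rule goes on to compare each randomized dose with pooled placebo by a linear mixed model for repeated measures in the ITT population. It reports the least-squares mean difference, 95% confidence interval and two-sided p-value at each visit.

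**SAP analysis.** SAP 8.3.2 specifies that model for ALT and AST and then lists further endpoints to be analysed similarly: lipids, NASH and fibrosis biomarkers, and eicosanoids. The eicosanoid bullet ends: "For eicosanoids, descriptive statistics will be presented without any statistical testing".

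**Record of changes.** SAP Section 9 sets out departures from the protocol, does not mention eicosanoids, and closes by saying that "no other changes were made to analyses specified in the protocol".

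**The concern.** The objective is comparative, but the planned output for this part of it is not. Group summaries alone give no estimate of the treatment difference and no interval around it, so a reader of the results could not say how large an effect the data support or exclude.

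There is also a problem of record. The SAP bullet contradicts the sentence that introduces its list and gives no reason. A programmer could follow either the lead-in or the bullet. Because Section 9 is silent, a reader who relies on it for departures from the protocol would not learn that a comparison covered by the protocol's rule had been removed.

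**Working it through.** No arithmetic applies: neither document gives an effect size, standard deviation or power for eicosanoids. The check is whether the protocol's rule reaches eicosanoids, and what the SAP then does with them.

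1. **Are eicosanoids secondary?** Yes by objective (Protocol 6.2, SAP 2.2) and by the SAP's own endpoint tier (SAP 4.1). The protocol's tier heading omits the word secondary, but that list is separate from the exploratory one.

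2. **Are they measured at multiple post-baseline visits?** Protocol Table 2 schedules the panel, for Cohorts 1 and 2, at baseline, Week 4, Week 12 and Early Termination. Scheduled on-treatment visits after baseline: Week 4 and Week 12, so two. The condition is met.

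3. **Does the protocol make an exception?** Protocol 13.2.2 names none. It covers eicosanoids by class, not by name.

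4. **What does the SAP leave?** SAP Section 7 defines the default description of continuous data by treatment group: n, mean, median, SD, quartiles, minimum and maximum. A between-group difference and its interval are not in that list.

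5. **What do neighbouring endpoints get?** Lipids and NASH/fibrosis biomarkers, in the same SAP list, keep the MMRM. SAP 8.3.3 analyses exploratory continuous endpoints in the same manner as the secondary ones. These include the metabolic parameters, among which SAP 2.3 counts adiponectin and resistin. Table 2 draws those two at the same visits as the eicosanoids. On a plain reading, exploratory markers with the same sampling schedule are modelled while this secondary panel is not.

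6. **Is the change recorded?** Section 9 goes down to the 29.5% rounding convention for responders, but has no entry for eicosanoids.

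7. **Does it touch the error rate?** The fixed sequence (SAP 7.3) holds only the primary and key secondary endpoints, each at 50 mg and then 25 mg. Eicosanoids are outside it, so neither the present text nor the fix changes the overall 0.05 level, the power statements or the sample size.

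**The case against.** The best case for the SAP has three parts.

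First, Protocol 13.2.2 leaves further detail on other secondary endpoints to the SAP, and describing a biomarker panel without tests is a defensible choice in a phase 2 trial. The choice is indeed open to the sponsor. But leave to add detail does not plainly extend to removing a comparison that the same section specifies, and it does not explain the silence in Section 9.

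Second, placebo is still shown beside each dose. That stands. A reader might infer that the placebo comparison disappears altogether, and the documents do not support that. A crude difference could be derived from the tabulated n, mean and SD. The estimate adjusted for baseline and diabetes status could not, and no difference of either kind is planned.

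Third, the SAP states that it was written to protocol version 6.0. The supplied protocol contains Cohort 3 and so appears to be version 7.0, the version cited in the SAP addendum. A reader might infer that the closing sentence of Section 9 is false. That cannot be established without the version 6.0 text. What can be said is that the sentence does not fit the supplied protocol, and that the later addendum, which deals with Cohort 3, does not reconcile the two.

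**Conclusion.** The point holds, as a minor one. For eicosanoids the SAP removes the model-based difference from pooled placebo, its 95% confidence interval and its p-value. The supplied protocol's class rule calls for these at both doses and at each visit. The SAP's list contradicts itself, and Section 9 does not record the change. The conclusion assumes that eicosanoids count as secondary under the protocol's rule, as its objective and the SAP's tier indicate, and that version 6.0 carried the same rule.

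Two larger readings are tempting and should not be drawn:

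- **That one of three secondary objectives is lost.** Both documents state a single secondary objective with three groups of measures, and the other two groups keep the model.
- **That a fixed number of contrasts is lost.** Four named eicosanoids at two doses give 4 × 2 = 8 at Week 12. But the protocol's rule reports every visit, which with Weeks 4 and 12 gives 4 × 2 × 2 = 16. Protocol 11.1.3.3 and SAP 8.3.2 also introduce the four as examples of what the panel includes, so four is not shown to be the total.

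**What to change.** Delete the descriptive-only sentence in SAP 8.3.2 and run the MMRM already specified there for the eicosanoids. The section's existing provisions for convergence problems and for transformation when model assumptions fail are enough; no new rule is needed. Report least-squares mean differences from pooled placebo with 95% confidence intervals and nominal p-values, labelled as unadjusted and outside the fixed sequence.

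If the sponsor keeps the descriptive approach, it should enter the change and its reason in SAP Section 9, amend the closing statement there, and take eicosanoids out of the list of endpoints analysed like ALT and AST.

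The first option costs one further run of an existing model per eicosanoid and a few more unadjusted p-values. The second costs a few lines of text but leaves this part of the objective without an estimated treatment difference. Neither affects alpha, power or sample size.

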8.3.3. Exploratory Efficacy Endpoints and Analyses

Analysis of exploratory endpoints will be based on the ATP. Exploratory efficacy endpoints include the change from baseline over the treatment period in following continuous measurements:

- Liver fibrosis, as determined by VCTE
- Metabolic parameters
- Anthropometric parameters including weight, waist and hip circumference, waist-hip ratio, and blood pressure
- Lipidomic analyses for DNL

Analyses will be performed similarly to those described in the secondary efficacy analysis section above.

The proportion of subjects with <5% liver fat (normalized) at Week 12 will be summarized by treatment group. Analyses similar to those described for the key secondary efficacy endpoint will be used.

Subset analyses will be performed on all exploratory efficacy endpoints for subjects enrolled in the US and China to evaluate the consistency of results between subjects enrolled in each country.

8.4. Pharmacokinetics (PK)

Blood samples for determination of TVB-2640 PK are to be collected immediately before and then at 2, 4, 6, and 24 hours after the first study drug dose; the 24-hour post-dose sample is to be collected on Day 2, immediately before the second study drug dose. Blood samples for PK also are to be collected immediately pre-dose and at 2, 4, and 6 hours post-dose at Week 2 (i.e., Day 8).

PK samples will be collected from 12 active subjects/cohort in the US and 8 active subjects in the 50 mg cohort in China.

PK analyses will be performed by a separate vendor and described outside of this SAP (i.e., in a separate PK SAP or other document).

8.5. Safety

Safety will be evaluated based on data collected for adverse events, vital signs, physical examinations, electrocardiogram (ECG), ophthalmologic examinations, and laboratory data. No

Sponsor: Sagimet Biosciences
Protocol Number: 3V2640-CLIN-005
Version and Date: Final Version 1, 02June2020

formal statistical testing will be conducted for the safety analyses. Descriptive statistics will be used to evaluate safety data in this study. Summaries will be presented by treatment group.

Subset analyses will be performed on all safety endpoints for subjects enrolled in China to evaluate the consistency of results between subjects enrolled in each country.

All safety analysis reporting will be based on the Safety Analysis Set. All safety data will be listed by treatment group and subject.

8.5.1. Adverse Events

An AE is any untoward medical occurrence in a patient or clinical investigation subject administered a pharmaceutical product, and which does not necessarily have to have a causal relationship with this treatment. An AE can therefore be any unfavorable and unintended sign (including abnormal laboratory findings), symptom, or disease temporally associated with the use of an investigational product, whether or not related to the investigational product.

An unexpected AE is any event for which the nature or severity is not consistent with the information in the current Investigator's Brochure.

Any abnormal clinical or laboratory finding considered by the Investigator to be clinically significant is to be recorded in the eCRF as part of the subject's medical history if occurring prior to the start of study drug administration and as an AE if occurring after the start of study drug administration at baseline, where the finding represents a change from baseline.

A treatment emergent AE (TEAE) is defined as any AE occurring after the first dose of study treatment. All summaries of AEs will be based on TEAEs. All AEs recorded on the eCRF, whether treatment emergent or not, will be presented in the data listing. Non-TEAEs will be flagged in the listings.

Adverse Events will be coded using MedDRA version 22.0 Mar 2019 for reporting by SOC and PT. Summaries of TEAEs by SOC and PT will be presented in descending order of overall incidence. TEAEs will also be summarized by maximum intensity as classified according to the National Cancer Institute (NCI) Common Terminology Criteria for Adverse Events (CTCAE), Version 5.0. If the AE is not included in the NCI CTCAE, then the Investigator is to determine the severity of the AE according to the criteria provided in the study protocol. The causal relationship of each AE to study drug will be determined by the Investigator according to best medical judgment as definitely related, probably related, possibly related, unlikely related, or unrelated. If the relationship between the AE and study drug is determined to be "possible", "probable", or "definite", the event will be considered to be treatment-related for the safety analyses.

Any missing severity assessments will be assumed to be Grade 3 (severe) and missing relationship assessments will be assumed to be related. All AE summaries will be produced using the safety population and displayed by treatment group and overall.

Sponsor: Sagimet Biosciences

Protocol Number: 3V2640-CLIN-005

Version and Date: Final Version 1, 02June2020

An overview of TEAEs will be produced, including counts and percentages of subjects with any incidences of: TEAEs, TEAEs related to study treatment, serious adverse events (SAEs), TEAEs leading to study drug discontinuation, SAEs, and fatal SAEs. The number of AEs will also be included on the summary.

In addition to the overview of TEAEs, the following summaries of AEs will be provided for the safety population by treatment group and overall:

- TEAEs by SOC and PT
- TEAEs related to study treatment by SOC and PT
- CTCAE Grade 3 or higher TEAEs by SOC and PT
- CTCAE Grade 3 or higher TEAEs related to study treatment by SOC and PT
- TEAEs leading to treatment discontinuation by SOC and PT

Summaries of TEAEs by SOC, PT, and maximum severity as well as TEAEs by SOC, PT, and maximum relationship to study treatment will also be prepared.

A comprehensive listing of all AEs will be provided in a by-subject data listing. AEs that began after 84 days of dosing will be identified on the listing. In addition, the following listings will be provided:

- TEAEs related to study treatment
- SAEs
- TEAEs leading to treatment discontinuation; and
- Fatal AEs.

